4.2.2 Handling of Withdrawals

When a patient withdraws from the study, the reason(s) for withdrawal shall be recorded by the investigator on the relevant page of the electronic case report form (eCRF). Patients lost to follow-up will be contacted by the site in an attempt to determine the reason for study withdrawal. A maximum of 3 telephone call attempts should be documented on different days.

Patients who withdraw from the study will not be replaced.

5 Study Treatments

This is an observational study in patients with T2DM. No study medications will be administered in this study. Patients enrolled in the study will have been under the care and treatment of their physician and will be treated according to their physician criteria and as per standard clinical practice. Alogliptin or alogliptin FDCs will have been prescribed as part of the patients' T2DM treatment program, independent of participation in this study. Alogliptin or alogliptin FDCs will be prescribed as determined by the physician and standard clinical practice. No intervention or change in the patients' T2DM management will be required as a result of this study.

6 Study Assessments and Collection of Data

Before collecting any data, all potential patients will sign an informed consent form (ICF). Patients will have the opportunity to have any questions answered before signing the ICF. The investigator must address all questions raised by the patient. The investigator will also sign the ICF. Refer to Section 8.3 for additional details on patient's consent.

Study assessments will be performed as outlined in this section and in the approximate time points indicated in the Data Collection Schedule (Table 12-1). The time points reflect the standard clinical practice, and patients will not be asked to travel to the site only for the purpose of this study (see Section 3.1).

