7.5 Sample Size Calculations

[figure not shown]
Sample size was calculated for the primary endpoint of the study: to evaluate the effect of Alogliptin or its FDCs on glycosylated hemoglobin (HbA1c) level in patients with diabetes mellitus type 2 (V3). Sample size was calculated using SAS 9.3 proc power procedure (power for Confidence Interval for Paired Mean Difference as for accuracy of parameter estimation) for following parameters (fixed scenario elements):

Fixed Scenario Elements	
Distribution	Normal
Method	Exact
Correlation	0.35
Nominal Prob(Width)	0.9
Number of Sides	2
Alpha	0.05
Prob Type	Conditional

Standard deviation was assessed based on S. Del Prato et al study and was considered to be at most 0.70% (for glycosylated hemoglobin level dynamics). To determine required number of patients values from 0.60% to 0.70% were taken. Desired half-wide for parameter estimation was set as range between 0.05 – 0.1. Following required number of pairs were calculated:

Computed N Pairs				
Index	Half-Width	Std Dev	Actual Prob(Width)	N Pairs
1	0.05	0.60	0.904	770
2	0.05	0.65	0.904	899
3	0.05	0.70	0.900	1037
4	0.06	0.60	0.904	542
5	0.06	0.65	0.903	632
6	0.06	0.70	0.903	729
7	0.07	0.60	0.906	404
8	0.07	0.65	0.902	470
9	0.07	0.70	0.904	542

10	0.08	0.60	0.902	313
11	0.08	0.65	0.907	365
12	0.08	0.70	0.905	420
13	0.09	0.60	0.905	251
14	0.09	0.65	0.906	292
15	0.09	0.70	0.907	336
16	0.10	0.60	0.904	206
17	0.10	0.65	0.902	239
18	0.10	0.70	0.904	275

For the worst-case scenario of half-width as 0.05, if Std Dev is 0.65, the required number of pairs is 899. Taking into account a possible dropout of 25%, to reach study objectives in regard to this endpoint, it is recommended to enroll at least 1199. If taking Std Dev as 0.60 or 0.70, the required number of pairs is from 770 or 1037. Taking into account a possible dropout of 25%, it is recommended to enroll at least 1027 or 1383 patients into the study.

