### 4.2. Secondary Endpoint

The secondary endpoints related to real-world clinical response to alogliptin or alogliptin FDCs are the following:

- Clinical response rates: incidence rates of responders. The following definitions of response will be used as secondary endpoints:
  - Change from baseline in HbA1c level on alogliptin or its FDCs therapy in subgroups with different clinical characteristics (V3).
  - HbA1c levels reduction to the goals of <7.0% (V3).
  - HbA1c reduction >0.3% with no tolerability findings (hypoglycemic event, or weight gain  $\geq 5\%$ ) (V3).
  - To evaluate the effect of alogliptin and its FDCs on fasting blood glucose dynamics in patients with diabetes mellitus type 2 over time (V1-V2-V3).
- To evaluate the effect of alogliptin or alogliptin FDCs on glycosylated hemoglobin (HbA1c) level dynamics in patients with diabetes mellitus type 2 in dependence on clinical characteristics (V1-V2-V3).
- ADRs, SAEs, and AESIs.

The secondary endpoints related to alogliptin or alogliptin FDCs utilization patterns are the following:

- Percentage of patients who remain on treatment with alogliptin or alogliptin FDCs (V2-V3).
- Time to alogliptin or alogliptin FDCs dose escalation or dose reduction (V2-V3).

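### Calls to patients lost to follow-up seek only the reason for leaving, so drug status and serious events may stay unknown, and the persistence percentage has no rule for such patients

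*Protocol*

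**What the plan says.** Protocol 4.2.2, repeated in SAP 8.2.1, gives the calls one purpose: "Patients lost to follow-up will be contacted by the site in an attempt to determine the reason for study withdrawal". The effort is capped: "A maximum of 3 telephone call attempts should be documented on different days". SAP 8.2.1 adds that missing data are not imputed.

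Persistence is a named secondary endpoint (Protocol 7.2). SAP 4.2 words it as "Percentage of patients who remain on treatment with alogliptin or alogliptin FDCs (V2-V3"). Protocol 7.8.2 and SAP 8.4.2 report it as frequencies and percentages with 95% confidence intervals. Protocol 7.6 and SAP 7.1 base the analysis on all enrolled patients.

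Other provisions bear on the point:

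- Footnote 4 of Table 12-1 permits medical records as a source for alogliptin dose and end date, other diabetes treatment, resource use and the safety report. In the follow-up period these items belong to the Month 3 and Month 6 columns.
- Protocol 6.2.3 requires an SAE to be reported within 24 hours of site staff learning of it.
- Protocol 6.2.2 ends the assessment of ADRs, AESIs and SAEs with study participation. Protocol 4.2 ends study duration at the last visit. The Protocol Abstract ends observation at loss to follow-up.
- The Abstract allows Kaplan-Meier curves for treatment patterns as an option.

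**The concern.** Stopping the drug is a plausible reason to stop attending, although the documents do not say so. If the two are linked, treatment status is missing most often in the patients whose status matters most for persistence. The site will already be trying to reach these patients by telephone, but the plan does not have it ask for the endpoint.

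Two results are exposed. The first is the persistence percentage, which depends on how unknown patients are counted. The second is the SAE count, which may miss events after the last attended visit unless they reach the site another way. Analysis of the collected data cannot recover a status that was never recorded; it can only show how far the answer might move.

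**Working it through.** **The plan's own figure.** The only dropout figure is in Protocol 7.5: "For the worst-case scenario of half-width as 0.05, if Std Dev is 0.65, the required number of pairs is 899", followed by "Taking into account a possible dropout of 25%, to reach study objectives in regard to this endpoint". The inputs are SD 0.65, "Correlation 0.35", two-sided alpha 0.05, "Nominal Prob(Width) 0.9" and the conditional method.

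- SD of the paired difference = 0.65 × √(2 × (1 − 0.35)) = 0.741.
- The smallest n for which the half-width is at most 0.05 with probability at least 0.90, given that the interval covers the true mean, is 899 (achieved 0.904), as stated.
- 899 / (1 − 0.25) = 1198.7, rounded up to 1199, as stated.
- 1199 − 899 = 300 patients, or 25.0%, are allowed to lack an HbA1c pair.

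The sample size is not in dispute. The 25% is an allowance for missing HbA1c pairs at Visit 3, not a rate of loss to follow-up or of unknown drug status.

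**Range for persistence.** Let u be the share of enrolled patients with unknown status and p the persistence among those with known status.

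- Lower bound (all unknown patients have stopped) = p(1 − u).
- Upper bound (all still on drug) = p(1 − u) + u.
- Width = u, whatever p and the sample size are. The lower enrolment figure of 1142 in SAP 3 therefore makes no difference.

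The documents give neither p nor u, so both are assumed:

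| u | p = 60% | p = 80% | p = 90% | Width (points) |
|---|---|---|---|---|
| 5% | 57.0–62.0% | 76.0–81.0% | 85.5–90.5% | 5 |
| 10% | 54.0–64.0% | 72.0–82.0% | 81.0–91.0% | 10 |
| 25% | 45.0–70.0% | 60.0–85.0% | 67.5–92.5% | 25 |

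**Comparison with the reported interval.** At u = 10% of 1199, about 1079 patients have known status. At p = 80% the 95% half-width is 1.96 × √(0.80 × 0.20 / 1079) = 2.4 points, a full width of 4.8 points. The 10-point range is about twice that, and the planned interval would not show it.

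**Direction of error.** Let q be the true persistence among unknown patients. True persistence is (1 − u)p + uq.

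- If unknown patients are dropped, the error is u(p − q): upward when q is below p.
- If they stay in an all-enrolled denominator as not remaining, the error is −uq: downward unless all had stopped.

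At u = 10% and p = 80%, q = 0 gives errors of +8 and 0 points respectively; q = 80% gives 0 and −8 points. The choice of denominator alone moves the reported figure from 80% to 72%.

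**What recovery of status would buy.** If u starts at 25% and status is recovered for 25%, 50% or 75% of those patients, the width falls to 0.25 × 0.75 = 18.75, 0.25 × 0.50 = 12.5 or 0.25 × 0.25 = 6.25 points. The documents support no particular recovery rate, and patients who withdraw consent cannot be counted as reachable.

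**The case against.** The strongest reply is that the plan has other routes to this information. Footnote 4 of Table 12-1 covers the very items at issue. The reason given for leaving may itself be a treatment stop or an adverse event. Any SAE mentioned on the call must be reported, and AEs volunteered by the patient are recorded. Patients who switch treatment are followed to the end of the study. Events after loss to follow-up also lie outside the declared observation window, so collecting them extends the design rather than correcting an error.

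Much of this stands. A reader might infer that status is unknown for every lost patient; the documents do not support that. The routes are nevertheless incomplete. The footnote is permissive, and no text extends it to missed visits. A patient who no longer attends may leave no record at the site. The withdrawal reasons in Protocol 4.2.1 name neither a treatment stop nor an adverse event. Optional Kaplan-Meier curves would censor lost patients, which is unbiased only if loss is unrelated to stopping.

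A reader might also take 25 points as the expected uncertainty. That is not supported: the 25% was set for HbA1c pairs and may include consent withdrawals or attending patients without a Visit 3 HbA1c, whose drug status may be known. SAP 9 further reports early termination, enrolment far below plan and missed visits, so the actual unknown share may differ from 25% in either direction.

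**Conclusion.** The point holds as a gap in data collection and in the definition of the persistence analysis. The calls are specified only for the withdrawal reason, no rule applies records to patients who miss visits, and no rule says how unknown status counts. The worst-case range equals the unknown share: 10 points at 10%, with a ceiling of 25 points that requires every assumed dropout to be unknown.

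A reader might infer that reported persistence will be too high. The documents do not settle this. It would be too high if unknown patients are dropped and are less often on drug than the rest, and too low if they stay in an all-enrolled denominator as not remaining.

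The SAE part is narrower: events after the last visit may go unrecorded, partly because the protocol closes the window there. This is a worthwhile improvement to a descriptive secondary endpoint and does not affect the primary sample size calculation.

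**What to change.** **Protocol 4.2.2.** At the same calls, and from medical records, record whether the patient still takes alogliptin or an FDC, the stop date if not, and any hospitalisation or SAE since the last visit. Exempt patients who have withdrawn consent. State that the records check also applies to patients who miss Month 3 or Month 6.

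**Protocol 4.2.2 and 6.2.2.** State that this contact counts as part of the observation period, so that what it yields belongs in the persistence and safety tables.

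**SAP 8.2.1 and 8.4.2.** Fix the denominator for persistence and the handling of unknown status. Report best- and worst-case bounds beside the percentage. Show visits missed through sponsor termination separately from patient loss.

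**Cost.** A few questions in a call already planned, one eCRF field group, the records check and extra table rows; no added visits. Changing the protocol may need an amendment with IEC/IRB approval (Protocol 10.2.1). If early termination means calls are no longer possible, the SAP changes still apply and need no new data.

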6.1 Study Assessments

6.1.1 Indication and Prescribing Physician-Related Data

The following information related to the drug indication and treating physician will be collected as shown in the Data Collection Schedule (Table 12-1):

- **Indication information:** alogliptin and alogliptin FDCs market status, T2DM standard of care
- **Prescribing physician-relevant information:** general/specialized practitioner

6.1.2 Demographic Data and Medical History

Patient demographic data will include date of birth (if allowed by local regulations), sex, race, ethnicity, height, and body weight.

Medical history will include general medical history (including medications, co-morbidities, and hospitalizations), as well as specific T2DM history (including date of diagnosis and previous treatments received).

Demographic data and medical history will be obtained from medical records and as shown in the Data Collection Schedule (Table 12-1).

6.1.3 Prior and Concomitant Medications

All prior and concomitant medications, including but not limited to T2DM treatments, will be collected and recorded in the eCRF as shown in the Data Collection Schedule (Table 12-1). Changes in all medication will also be collected.

For each prior and concomitant medication, the following information will be collected: medication name, start date, dose, and end date.

6.1.4 Clinical Response to Treatment With Alogliptin or Alogliptin Fixed-Dose Combinations

6.1.4.1 HbA1c

The latest HbA1c value available before the starts of alogliptin or alogliptin FDC (but within 3 months before the first dosage) will be considered the baseline value.

The HbA1c level goal for the patient will be collected at baseline, when determined as part of standard clinical practice.

Clinical response to treatment with alogliptin or alogliptin FDCs will be evaluated based on HbA1c levels, as per the following endpoints:

- Change from baseline in HbA1c levels.
- Change in HbA1c levels over time
- Clinical response rates: incidence rates of responders. The following definitions of response will be used:
 - HbA1c level reduction to the goals of <7.0%.
 - HbA1c reduction >0.3% with no tolerability findings (hypoglycemic event, or weight gain $\geq 5\%$) (Mathieu et al 2013).

The HbA1c levels will be recorded in the eCRF as shown in the Data Collection Schedule (Table 12-1). The HbA1c levels will be obtained from any assessments performed as per standard clinical practice. No study-specific measurements will be performed. If multiple HbA1c levels are available, then the assessment closest to the visit time point will be used.

6.1.4.2 Other Assessments Related to Clinical Response

Data for other assessment related to clinical response will be collected as shown in the Data Collection Schedule (Table 12-1) and will include the following:

- To evaluate the effect of alogliptin and its FDCs on fasting blood glucose dynamics in patients with diabetes mellitus type 2 over time (V1-V2-V3)
- Incidence of newly diagnosed co-morbidities and complications.
- Body weight: this information will be obtained from any assessments performed as per standard clinical practice. No study-specific measurements will be performed.
- Healthcare resources utilization: number of hospitalizations (including length of stay during each hospitalization, reason, and urgency [urgent/not urgent]), emergency room visits, and physician office visits.

6.1.5 Utilization of Alogliptin, Alogliptin Fixed-Dose Combinations, and Other Type 2 Diabetes Mellitus Therapies

Data on the use of alogliptin and alogliptin FDCs will include start date, dose, and end date. Information will also be collected on any additional T2DM treatment, both added in combination to alogliptin or due to switching treatment from alogliptin or alogliptin FDCs to another T2DM treatment. Additional T2DM treatment may include glucagon-like peptide-1 agonists, other oral glucose lowering agents, injectable insulin, other insulins, and other injectable glucose lowering agents.

Information on alogliptin, alogliptin FDCs, and other T2DM treatments will be collected as shown in the Data Collection Schedule (Table 12-1).

6.2 Safety Assessments

The investigator or site staff will be responsible for eliciting, documenting, and reporting events that meet the definition of ADR, AESI, or SAE, as described in Sections 6.2.1 to 6.2.5. Any AE volunteered by the patient will also be recorded.

6.2.1 Definitions of Adverse Events

An AE is defined as any untoward medical occurrence in a patient enrolled into this study regardless of its causal relationship to treatment.

An ADR is defined as any response to a medicinal product that is noxious and unintended and that occurs at doses normally used in humans for the prophylaxis, diagnosis, or therapy of diseases or for the restoration, correction, or modification of physiological function. Response in this context means that a causal relationship between a medicinal product and an AE is at least a reasonable possibility. Adverse reaction also includes adverse clinical consequences associated with use of the product outside the terms of the Summary of Product Characteristics or other conditions laid down for the marketing and use of the product (including prescribed doses higher than those recommended, overdoses, or abuse).

An SAE is defined as any untoward medical occurrence that, at any dose:

1. Results in DEATH.
2. Is immediately LIFE THREATENING. The term “life threatening” refers to an event in which the subject was at risk of death at the time of the event; it does not refer to an event that hypothetically might have caused death if it were more severe.
3. Requires inpatient HOSPITALIZATION or prolongation of existing hospitalization.
4. Results in persistent or significant DISABILITY/INCAPACITY.
5. Is a CONGENITAL ANOMALY/BIRTH DEFECT.
6. Is an IMPORTANT MEDICAL EVENT that satisfies any of the following:
 - a. May require intervention to prevent items 1 through 5 above.
 - b. May expose the subject to danger, even though the event is not immediately life threatening or fatal or does not result in hospitalization.
 - c. Includes any event or synonym described in the Takeda Medically Significant AE List (Table 6-1).

Table 6-1 Takeda Medically Significant AE List

Term	
Acute respiratory failure/Acute respiratory distress syndrome (ARDS)	Hepatic necrosis
Torsade de pointes/Ventricular fibrillation/Ventricular tachycardia	Acute liver failure
Malignant hypertension	Anaphylactic shock
Convulsive seizure	Acute renal failure
Agranulocytosis	Pulmonary hypertension
Aplastic anaemia	Pulmonary fibrosis
Toxic epidermal necrolysis/Stevens-Johnson syndrome	Neuroleptic malignant syndrome/Malignant hyperthermia
	Spontaneous abortion/stillbirth and fetal death
	Confirmed or suspected transmission of infection agent by a medicinal product
	Confirmed or suspected endotoxin shock

The following AEs will be considered AESIs: pancreatitis, hepatic disorders, and hypersensitivity reactions (including angioedema, anaphylaxis, and Stevens-Johnson syndrome). Targeted follow-up forms have been developed to further guide the collection of data of AESIs and the forms need to be submitted to the sponsor as part of the AE source documents.

6.2.2 Eliciting and Documenting Adverse Events

Adverse drug reactions, AESIs, and SAEs will be assessed from the time the patient signs the ICF until the end of study participation. Any AE volunteered by the patient will also be recorded.

The investigator is responsible for following SAEs and AESIs until resolution, until the patient returns to baseline status, or until the condition has stabilized with the expectation that it will remain chronic, even if this extends beyond study participation.

6.2.3 Reporting Adverse Events

All ADRs, AESIs, and SAEs reported or observed during the study, as well as any AE volunteered by the patient, will be recorded on the AE page of the eCRF. Information to be collected includes drug treatment, dose, event term, time of onset, investigator-specified

assessment of severity and relationship to study drug, time of resolution of the event, seriousness, any required treatment or evaluations, and outcome. Adverse drug reactions, AESIs, and SAEs resulting from concurrent illnesses, reactions to concurrent illnesses, reactions to concurrent medications, or progression of disease states must also be reported. The Medical Dictionary for Regulatory Activities (MedDRA) will be used to code all AEs.

Any medical condition that is present at baseline but does not deteriorate should not be reported as ADRs, AESIs, or SAEs. However, if it deteriorates at any time during the study, it should be recorded as an ADR, AESI, or SAE.

Any AE that meets SAE criteria (Section 6.2.1) must be reported to Takeda immediately (i.e., within 24 hours) after the time site personnel first learn about the event. Any ADR or AESI must be reported to Takeda within 1 business day after the time site personnel first learn about the event. Adverse events of special interest will be followed up with specific target forms provided by Takeda. The (S)AEs will be reported by telephone and faxing the appropriate forms to Takeda. After office hours, the emergency telephone number is the one of Takeda as mentioned in the appropriate (S)AE forms.

6.2.4 Assessment of Severity

The severity, or intensity, of an AE refers to the extent to which an AE affects the patient's daily activities. The intensity of the AE will be rated as mild, moderate, or severe using the following criteria:

Mild: An event usually transient in nature and generally not interfering with normal activities.

Moderate: An AE that is sufficiently discomforting to interfere with normal activities.

Severe: An AE that is incapacitating and prevents normal activities.

Changes in the severity of an AE should be documented to allow an assessment of the duration of the event at each level of intensity to be performed. Adverse events characterized as intermittent do not require documentation of onset and duration of each episode.

6.2.5 Assessment of Causality

The investigator's assessment of an AE's relationship to study drug is part of the documentation process, but it is not a factor in determining what is or is not reported in the study. If there is any doubt as to whether a clinical observation is an AE, the event should be reported.

The relationship or association of alogliptin or alogliptin FDCs in causing or contributing to the AE will be characterized using the following classification and criteria:

Unrelated: This relationship suggests that there is no association between the study drug and the reported event.

Possible: This relationship suggests that treatment with the study drug caused or contributed to the AE, ie, the event follows a reasonable temporal sequence from the time of drug administration or follows a known response pattern to the study drug, but could also have been produced by other factors.

Probable: This relationship suggests that a reasonable temporal sequence of the event with drug administration exists and, based upon the known pharmacological action of the drug, known or previously reported adverse reactions to the drug or class of drugs, or judgment based on the investigator's clinical experience, the association of the event with the study drug seems likely. The event disappears or decreases on cessation or reduction of the dose of study drug.

Definite: This relationship suggests that a definite causal relationship exists between drug administration and the AE, and other conditions (concurrent illness, progression/expression of disease state, or concurrent medication reaction) do not appear to explain the event. The event reappears or worsens if the study drug is re-administered.

